## **8.3 Missing Data Approaches**

The primary analysis will be conducted using the available data without any statistical imputation for missing data for data lost to follow up or otherwise unavailable. Accordingly, it is assumed for the primary analyses that missing primary outcomes are missing completely at random. We will examine the proportion of missing primary outcome data to ensure that the missing rate is comparable across the two treatments.

Analysis of the secondary objectives will generally include available data such that no data obtained within the study assessments windows will be discarded and no imputation for missing data will be done.

## 8.4 Other Analysis

All other analyses of outcomes not described in the primary or secondary outcomes are exploratory in nature; therefore, resulting p-values and confidence intervals will generally be provided for descriptive purposes only. All p-values provided for any baseline and demographic characteristics will be for descriptive purposes only. As such, unless otherwise specified, p-values presented will be on a per analysis basis, with no further control for multiple tests.

For model building activities, p-values will be used to identify the best fitting model as well as covariates to be included in the final models. For these model building activities, p-values <0.05 will generally determine significance. However, due to the exploratory nature of these models, less rigid standards may be considered and would be described fully in the final clinical study report and study manuscript.

## **8.6 Secondary Analyses**

All secondary analyses will be performed according to both the intent-to-treat and per-protocol principle.

### **8.6.1 Explore the Association between the Main Outcome and Other Potential Confounding Variables**

An analogous model to the one described in section 8.5 will be run as a sensitivity analysis; however, additional covariates (e.g. effect modification or confounder) may be included in the model. Covariates to be examined will include:

- Taking specific concomitant medications (stimulant, sleeping medication, anticonvulsant, antidepressant, anxiolytic, nicotine, antihypertensive, antipsychotic, and opioid),
- Concurrent behavioral health therapy (defined as an affirmative response to PTSDTx30DCONT),
- Participant self-assessment of intervention (SGB vs. Sham),
- Post-block Horner's (HRNRSCOR\_POST), and

- Duration of PTSD (derived from DxMonth and DxYear for formal diagnoses or SxMonth and SxYear for symptom presence)

Other additional covariates may be considered for inclusion into the model based on a univariate analysis to investigate if any other measures are significantly associated with change in baseline to week 8 CAPs (where the p-value is less than 0.05). The study team will identify the list of potential covariates to include in the base model.

Each covariate will be included in the ‘full’ model as a confounder or effect modifier (an interaction term of the covariate with treatment arm will be included in the model). To simplify the full model, non-significant ( $p > 0.05$ ) covariates will be removed and reduced models will be run and compared against the full model. A final parsimonious model will be selected via two model fit indices: Akaike information criterion (AIC) and Bayesian information criterion (BIC).

### 8.6.2 Evaluate Treatment Effects on PTSD symptoms (via PCL-5 score) Across Time

The treatment effect on the clinical criteria of PTSD as measured by the PCL-5 over time will be assessed at weeks 2, 4, 6 and 8 using a generalized-linear mixed model to account for temporal correlation between weekly measures and the clustering of the data; this model will control for treatment, week, site, baseline PCL-5 score and the two way interaction between treatment and time (see below for proposed model). The outcome variable will be the continuous PCL-5 score obtained at each visit. A sensitivity analysis will also be run by treating the outcome variable as a binary indicator of positive PTSD diagnosis (score of 33 or greater suggests positive screening for PTSD) (National Center for PTSD, 2017).

$$Y_{ij} = \alpha + \beta_1 \text{Time}_{ij} + \beta_2 \text{Site}_{ij} + \beta_3 \text{Treatment}_{ij} + \beta_4 \text{BaselinePCL5}_{ij} + \beta_5 (\text{Time} \times \text{Treatment})_{ij} + s_i + \varepsilon_{ij}$$

Where  $Y_{ij}$  is the  $j^{\text{th}}$  measure of PCL-5 in subject  $i$ ,  $\alpha$  is the intercept,  $\beta_1$  through  $\beta_5$  are coefficients,  $s_i$  is a random subject effect and  $\varepsilon_{ij}$  is the residual error term. Statistical analysis modeling will be carried out utilizing SAS/STAT PROC MIXED (Littell, Milliken, Stroup, Wolfinger, & Schabenberger, 2006) with the general structure of the SAS code for this model shown below. Adjusted estimates of the PCL-5 scores at each visit between the two arms and corresponding 95% confidence intervals will be produced.

```
proc mixed data = Secanaly_sgb;
class Unique_ID timepointN Treat site;
model PCL5_TotalScore = timepointN Treat BL_Score timepointN*Treat/s;
random int / subject= Unique_ID;
repeated timepointN / type=cs subject=Unique_ID;
estimate 'Intervention Effect of SGB' Treat 1 -1;
lsmeans timepointN* Treat;
run;
```

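### The illustrative PROC MIXED code in SAP 8.6.2 leaves site out of the MODEL statement and requests no confidence intervals, although the section's text promises both

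*SAP*

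**What the plan says.** SAP 8.6.2 describes the PCL-5 analysis over weeks 2, 4, 6 and 8 in words, as an equation and as SAS code.

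- **Words:** "this model will control for treatment, week, site, baseline PCL-5 score and the two way interaction between treatment and time". The continuous PCL-5 score is the outcome.
- **Equation:** it contains a Site term. Its random part is s_i, which "is a random subject effect and" a residual error term.
- **Output:** "Adjusted estimates of the PCL-5 scores at each visit between the two arms and corresponding 95% confidence intervals will be produced".
- **Code:** it is introduced "with the general structure of the SAS code for this model shown below". CLASS lists site. The model line is "model PCL5_TotalScore = timepointN Treat BL_Score timepointN*Treat/s". The covariance lines are "random int / subject= Unique_ID" and "repeated timepointN / type=cs subject=Unique_ID". The output comes from one ESTIMATE statement (Treat 1 -1) and "lsmeans timepointN* Treat".

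Three other places bear on this. Protocol 5.1 stratifies randomisation by site. The code in SAP 8.5 has site in MODEL and requests intervals twice (clparm, and cl on LSMEANS). SAP 8.6.3 sends the K6, GAD-7, PHQ-9, SF-12, pain and M.I.N.I.-Plus outcomes to techniques similar to those of 8.6.2, and names site again in its text.

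**The concern.** The words and the code describe different analyses. A CLASS variable that is used in no later statement does nothing, so the printed code fits a model without the stratum that the SAP says it controls for. PROC MIXED prints estimates, standard errors and tests by default, but gives confidence limits only when asked, and the code does not ask.

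A programmer may well start from the printed code, and 8.6.3 reuses the approach for further outcomes, so the omission could spread. At stake are the reported precision of the secondary results, their protection against dropout that differs by site and arm, and whether the promised intervals appear in the output.

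**Working it through.** The plan gives no figure of its own here, so the check compares the statements and then sizes the consequence. SAS was not run; statements about its output rest on its standard behaviour.

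**1. Text against code**

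| Element | 8.6.2 text or equation | 8.6.2 code | 8.5 code |
|---|---|---|---|
| Site as a covariate | yes | CLASS only | in MODEL |
| Options requesting 95% CIs | CIs promised | 0 | 2 |
| Random part | subject effect + residual | RANDOM int and REPEATED type=cs | not applicable |

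**2. Which arm differences the code prints.** The output sentence can mean arm means or arm differences at each visit.

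- *Arm means:* LSMEANS prints all eight (4 visits x 2 arms) with standard errors but without intervals.
- *Arm differences:* the ESTIMATE line gives only the average over the four visits. Under last-level reference coding, with visits sorted by week, the Treat coefficient printed by /s is the week-8 difference, again without an interval. Weeks 2, 4 and 6 each need Treat plus an interaction coefficient, and no statement requests that sum. So 1 of 4 differences appears indirectly and 3 of 4 are not requested.

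**3. Reported standard error when site is left out.** Assume that site explains a share s of the residual variance at a visit. The documents give no value, so a range is used. Without site, that share stays in the error term:

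week-8 SE ratio = 1/sqrt(1 - s); size of a nominal 5% test = 2 x Phi(-1.96 x ratio)

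| s | SE ratio | Test size | Coverage of a 95% CI |
|---|---|---|---|
| 2% | 1/sqrt(0.98) = 1.010 | 4.8% | 95.2% |
| 5% | 1/sqrt(0.95) = 1.026 | 4.4% | 95.6% |
| 10% | 1/sqrt(0.90) = 1.054 | 3.9% | 96.1% |

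For the contrast averaged over four visits, with between-visit correlation r (assumed 0.5 to 0.8), the ratio is sqrt(v/(v - s)) with v = (1 + 3r)/4. At r = 0.5, v = 0.625, giving 1.016, 1.043 and 1.091 for s = 2%, 5% and 10%. At r = 0.8, v = 0.85, giving 1.012, 1.031 and 1.065.

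In points, with the planned 160 and 80 participants and an assumed SD of 15: SE without site = 15 x sqrt(1/160 + 1/80) = 2.054. With site and s = 10%, it is 2.054 x sqrt(0.90) = 1.949. The 95% half-widths are 1.96 x 2.054 = 4.03 and 1.96 x 1.949 = 3.82, a gap of 0.21 points in the conservative direction.

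**4. Actual precision with complete data.** In 20,000 simulated trials (week 8 only, least squares, SD 15, s = 10%, no missing data), the actual SD of the estimate with three equal sites was 1.943 with or without site. The mean reported SE was 1.940 with site and 2.046 without. With sites of 120, 70 and 50, the actual SD was 1.957 both ways, and the reported SE was 1.946 and 2.052. Monte Carlo error of these SDs is about 1/sqrt(2 x 20,000) = 0.5%. Only the reported SE changes.

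**5. Dropout that differs by site and arm.** Protocol 8.4 contemplates attrition as high as 25%. Illustration, all values assumed: SD 15, s = 10%, three equal sites with effects -5.81, 0 and +5.81 (mean square 2 x 5.81^2/3 = 22.5 = 10% of 15^2). Across the sites, 10/25/40% of active and 40/25/10% of sham participants have no follow-up, which is 25% in each arm. The mean site effect among those retained is 5.81 x (0.60 - 0.90)/2.25 = -0.77 for active and +0.77 for sham. Without site in the model, the arm difference shifts by about 1.55 points.

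**6. Covariance.** RANDOM int and REPEATED type=cs on the same subject give V = gJ + cJ + s2I. That is three parameters, but the derivative matrix has rank 2, so only g + c and s2 are identified. For example, (g, c) = (60, 0), (30, 30) and (0, 60) with s2 = 40 all give variance 100 and covariance 60. The fitted marginal covariance is the same as with either statement alone.

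**The case against.** The best defence is that the code is explicitly illustrative. The text and equation govern, both include site, the text promises the intervals, and 8.6.3 names site again. No passage says the code was run verbatim. This stands, and it is why the point ranks low. It does not remove the mismatch: a main effect named in the text, and the output promised just before the code, are part of a model's structure.

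The size is also modest. The site shares, the SD and the correlations are assumptions, and the largest week-8 case widens the interval by about 0.2 points. That is fair.

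A reader might go further than the documents allow in five ways:

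- **That the PCL-5 results were produced without site.** The second SAP addendum says the secondary analyses were conducted with mixed models, but not with which program. This has to be checked, not inferred.
- **That omitting site biases the comparison or loses precision.** With complete data, or missingness unrelated to site by arm, it does neither. The opposite blanket claim, that it can never bias, fails too once dropout differs by site and arm.
- **That three visit differences are missing outright.** This holds only if the output sentence means arm differences. If it means arm means, only a display option is absent, and the intervals follow from the printed SE and degrees of freedom.
- **That Protocol 8.2 requires site in this very model.** It lists site, but for a binary PCL-5 outcome, which SAP 8.6.2 treats as a sensitivity analysis.
- **That the doubled covariance term damages the analysis.** It changes no estimate and no model-based standard error; at most it may trigger a convergence or Hessian warning.

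**Conclusion.** The mismatch is real and can be verified within SAP 8.6.2. Run as printed, the code does not fit the stated model and does not print the promised intervals. The reported week-8 standard error would be about 1%, 3% or 5% too large for an assumed site share of 2%, 5% or 10%, making tests and intervals slightly conservative. Bias arises only if dropout differs by site and arm; the 1.55-point shift above illustrates a deliberately uneven pattern and is not an estimate for this trial.

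This is a correction the sponsor could make, not one on which the trial depends. The outcome is secondary, the written model is right, and the primary code in 8.5 already includes site and interval options.

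**What to change.** Make the code match the text:

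- `model PCL5_TotalScore = timepointN Treat site BL_Score timepointN*Treat / s cl;`
- Add `/ cl` to the existing ESTIMATE and LSMEANS statements.
- Add four same-visit contrasts. For week 8: `estimate 'SGB-sham wk 8' Treat 1 -1 timepointN*Treat 0 0 0 0 0 0 1 -1 / cl;`. For weeks 2, 4 and 6, move the interaction pair `1 -1` to the first, second and third position. This assumes that the four follow-up visits are the only time levels, sorted by week, with SGB first as in the 8.5 code.
- Avoid an unrestricted LSMEANS diff: eight cells give 8 x 7/2 = 28 pairs, of which only four are same-visit arm differences.

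Then confirm that the programs actually run for 8.6.2 (PCL-5) and for the 8.6.3 outcomes include site.

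Optional tidy-up: keep RANDOM int, which matches the equation, and delete the redundant REPEATED type=cs line.

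Cost: one term and one option in MODEL, CL on two statements, four ESTIMATE lines and a check of existing programs. No new data are needed.

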## 2. OBJECTIVES

### 2.1. Clinical Effectiveness Trial

The primary objective of the effectiveness study is:

- to evaluate whether right-sided SGB performed at 0 and 2 weeks will improve the CAPS-5 total symptom scores between baseline and 8 weeks

The secondary objectives of this study are:

- to evaluate whether right-sided SGB performed at 0 and 2 weeks will improve PTSD symptoms as reflected by corresponding PCL-5 items between baseline and 8 weeks
- to explore the association between the main outcome and potential confounding variables (e.g., concomitant medications, duration of PTSD, post-block Horner's syndrome, etc.)
- to evaluate whether right-sided SGB performed at 0 and 2 weeks will reduce distress (K6), suicidality (M.I.N.I.-Plus Suicidality), anxiety (GAD-7), depression (PHQ-9), alcohol use (AUDIT-C/AUDIT) or pain (short pain scale) between baseline and 8 weeks
- to evaluate whether right-sided SGB performed at 0 and 2 weeks will improve physical and mental (SF-12) condition between baseline and 8 weeks

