### 8.6.3 Evaluate Treatment Effects on Suicidal Thoughts (via M.I.N.I.-Plus Suicidality), Psychological Distress (via the K6), Anxiety Disorders (via GAD-7), Depression (via PHQ-9), Physical and Mental Composite Measures (via SF-12), and Pain (via Short Pain Scale) Across Time

Treatment effect in the improvement or reduction of relevant health and psychological status information such as suicidal thoughts (M.I.N.I.-Plus Suicidality), psychological distress (K6), anxiety disorders (GAD-7), depression (PHQ-9), physical and mental composite measures (SF-12), and pain (short pain scale) will be analyzed using similar modeling techniques as mentioned in section 8.6.2. Modeling techniques with either linear mixed models or generalized mixed models will account for the structure of the outcome measure (continuous, binary, ordinal, nominal). Each model will incorporate treatment, baseline measure, site, time (as categorical variable) and two-way interactions between treatment and time. Other potential covariates or effect modification variables may be included in the model based on a univariate analysis of baseline measures with the specific outcome measure of interest.

Another secondary analysis of interest is to determine the effectiveness of the SGB among the participants for whom the stellate ganglion was anesthetized effectively. The population that will be utilized for this analysis will be defined as the “Horner’s responder population.” This population will be defined as those participants who showed a maximum density of Horner’s syndrome, reflected by scleral injection, meiosis, and ptosis, following the procedure. For analytic purposes, this will include all participants with a Post-Horner’s total score of 12. The analytic approach will mirror that for the primary analysis but will utilize only Horner’s responders from the active treatment arm, with propensity scores based on baseline demographic and clinical characteristics used to define a comparator control population.

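### The PCL-5 mixed model forces equal variance, equal correlation and one baseline slope across weeks 2 to 8 with no check or fallback, so visit-specific confidence intervals may be miscalibrated in a direction the documents do not settle

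*SAP*

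**What the plan says.** SAP section 8.6.2 states that the treatment effect on PCL-5 "will be assessed at weeks 2, 4, 6 and 8 using a generalized-linear mixed model". The outcome is the continuous score. The fixed part is coded as "model PCL5_TotalScore = timepointN Treat BL_Score timepointN*Treat/s", so baseline enters once, with the same slope at every visit. The covariance is set by two statements, "random int / subject= Unique_ID" and "repeated timepointN / type=cs subject=Unique_ID".

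The section then commits to visit-level inference: "Adjusted estimates of the PCL-5 scores at each visit between the two arms and corresponding 95% confidence intervals will be produced". The only coded ESTIMATE is the treatment main effect, which averages over visits. The code is introduced "with the general structure of the SAS code for this model shown below", but no other covariance, selection rule, empirical standard error or covariance sensitivity analysis is named.

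SAP section 8.6.3 says the other secondary outcomes "will be analyzed using similar modeling techniques as mentioned in section 8.6.2", again without naming a covariance structure. Protocol section 2.1 ties the PCL-5 objective to week 8: SGB "will improve PTSD symptoms as reflected by corresponding PCL-5 items between baseline and 8 weeks". SAP section 2.1 words the same objective as an effect over time.

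**The concern.** Under compound symmetry every visit has the same residual variance, so the fitted standard error at each visit is built from a variance pooled over visits. If the true residual variance is not flat, the standard error is wrong at individual visits even though it is right on average.

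The single baseline slope adds to this. If the PCL-5 correlation with baseline changes between weeks 2 and 8, the variance left after baseline adjustment changes too, even when the raw SD does not.

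What is at stake is the calibration of the week-by-week PCL-5 intervals, including week 8, the time point in the protocol objective. Deleting either the RANDOM or the REPEATED statement does not help, because each alone still gives compound symmetry.

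**Working it through.** **Inputs from the documents.** Four modelled visits (SAP 8.6.2); 160 active and 80 sham (Protocol 6.1); type I error 0.05, taken as two-sided (Protocol 8.3); up to 25% attrition (Protocol 8.4). The documents give no PCL-5 SD, no visit-to-visit correlation and no interval width, so there is no figure of the plan's to reproduce. The only planning SD is 25, for CAPS-IV. All PCL-5 SDs, correlations and dropout timings below are assumptions.

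**Step 1: covariance pattern.** The random intercept adds a constant a to every element of the 4 × 4 matrix, and compound symmetry adds its own constant c. Only a + c enters the likelihood, so the two statements together still give one variance and one correlation.

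**Step 2: effect on visit intervals, complete data.** Let v_t be the residual variance at visit t and v̄ its mean over visits. Then

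- model SE = √(v̄ × (1/160 + 1/80)) = √(v̄ × 0.01875)
- true SE = √(v_t × 0.01875)
- ratio = √(v̄ / v_t); coverage = 2Φ(1.96 × ratio) − 1.

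Example with residual SD 12, 14, 16, 18: v̄ = (144 + 196 + 256 + 324)/4 = 230 and model SE = √4.3125 = 2.077. True SE at week 8 is √(324 × 0.01875) = 2.465 (ratio 0.84). At week 2 it is √(144 × 0.01875) = 1.643 (ratio 1.26).

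| Assumed residual SD, weeks 2, 4, 6, 8 | Week 2 ratio, coverage | Week 8 ratio, coverage |
|---|---|---|
| 15 throughout, AR(1) correlation 0.8 or 0.6 | 1.00, 95.0% | 1.00, 95.0% |
| 12, 14, 16, 18 | 1.26, 98.7% | 0.84, 90.1% |
| 18, 16, 14, 12 | 0.84, 90.1% | 1.26, 98.7% |
| 12, 17, 17, 12 | 1.23, 98.4% | 1.23, 98.4% |
| 14 rising to 16 | 1.07, 96.5% | 0.94, 93.4% |

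The first row shows that unequal between-visit correlation alone does no harm with complete data.

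**Step 3: single baseline slope, raw SD constant at 1.** With correlations r_t to baseline, the pooled slope is b = mean(r_t) and v_t = 1 − 2b·r_t + b². Type I error = 2(1 − Φ(1.96 × ratio)).

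- r = 0.8, 0.7, 0.6, 0.5: b = 0.65; v = 0.3825, 0.5125, 0.6425, 0.7725; v̄ = 0.5775. Week 8: ratio √(0.5775/0.7725) = 0.865, so the SE is 13.5% too small and type I is 0.090. Week 2: ratio 1.23, type I 0.016.
- r = 0.75 to 0.60 in equal steps: v̄ = 0.5444, week-8 v = 0.6456, ratio 0.918, type I 0.072.
- r = 0.70 to 0.55: v̄ = 0.6094, week-8 v = 0.7031, ratio 0.931, type I 0.068.
- No decay: ratio 1, type I 0.050.

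Simulation of 2,000 null trials per setting gave 0.095, 0.066 and 0.074 for the three decay settings. This agrees within Monte Carlo error (standard error about 0.006).

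**Step 4: falling raw SD.** Keep r = 0.75 to 0.60 but let raw SD s_t fall in equal steps, so b = mean(r_t·s_t) and v_t = s_t² − 2b·r_t·s_t + b². A 15% fall by week 8 gives v̄ = 0.4650, week-8 v = 0.4762 and type I 0.053. A 20% fall gives 0.4414, 0.4269 and 0.046, which reverses the direction.

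**Step 5: dropout completely at random, 5%, 12%, 18%, 25% by weeks 2, 4, 6, 8, AR(1) 0.8.** Constant SD: week-8 ratio 0.98, coverage 94.5%. SD 12 to 18: week 8 0.81, 88.9%. SD 18 to 12: week 2 0.86, 90.8%.

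**Step 6: visit-averaged contrast.** Ratio 1.00 in every complete-data case, and between 0.97 and 1.03 with dropout.

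**Step 7: scales with only weeks 4 and 8.** The Step 3 formulas with r = 0.7 and 0.5 give b = 0.6, v = 0.52 and 0.76, v̄ = 0.64, and week-8 type I 0.072. With 0.70 and 0.60 it is 0.063.

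**The case against.** The best defence has four parts. The code is offered as a general structure for a secondary outcome. The SAP frames its objectives as effects over time. The one coded contrast averages over visits and stays calibrated. Empirical standard errors would serve as well as an unstructured covariance. The last two points stand, and the first two lower the priority. They do not close the gap, because the SAP also promises intervals at each visit and names no other structure.

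A reader might infer three stronger things that the documents do not support.

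- That week-8 intervals are too narrow and week-2 intervals too wide. This needs residual variance to rise over time. Decaying correlation with baseline is a plausible route, but the documents give no visit variances or correlations, and Steps 2 and 4 show that falling variance reverses the result.
- That any departure from constant correlation is harmful. With complete data it is not; with the dropout tested, the week-8 standard error is about 2% too small.
- That every secondary model is affected over weeks 2 to 8. Only the PCL-5 code names compound symmetry; for the rest it is an inference from the word similar. GAD-7, PHQ-9, SF-12 and pain have only weeks 4 and 8 after baseline, so they have no week-2 estimate and a single correlation. K6 timing differs between Protocol Table 1 (all visits) and SAP section 3 (weeks 0, 4 and 8).

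**Conclusion.** The point holds for the visit-specific PCL-5 intervals. The model assumes a common residual variance, correlation and baseline slope, and nothing in the plan would reveal or correct a failure of that assumption. If residual variance varies by visit, intervals are too narrow where it is above average and too wide where it is below. Coverage at the worse visit is about 89 to 90% when SD moves between 12 and 18, and about 93% for a 14-to-16 change. Week-8 type I error is about 0.07 to 0.09 in the baseline-decay illustrations and 0.05 without decay.

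These sizes rest on assumed SDs and correlations, complete data or dropout completely at random, and large-sample approximations. The direction in this trial is unknown. The visit-averaged contrast is essentially unaffected, and the primary CAPS-5 analysis, which uses a single follow-up, is not involved.

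**What to change.** In the PCL-5 model, drop the RANDOM statement, change the REPEATED statement to `type=un`, add `BL_Score*timepointN` to the MODEL statement and use `DDFM=KR`. Name the fallback in advance if the model does not converge: heterogeneous Toeplitz, or empirical standard errors. In the simulations, allowing visit-specific variances brought week-8 type I error to between 0.046 and 0.054.

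State in section 8.6.3 which covariance the continuous outcomes use. If similar techniques is read as carrying compound symmetry over, apply the same change there. For scales measured only at weeks 4 and 8, this means allowing unequal variances at the two visits.

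Both SAP addenda postdate unblinding, so report the revised model beside the specified one rather than in its place.

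The cost is a few lines of code and a sentence or two of SAP text. Four visits need 4 variances + 6 covariances = 10 parameters, which about 240 participants can readily support. The one added burden is the named fallback.
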